8.1.3 The SCCHN Cohort Expansion (Part 2; Completed)

A total of approximately 35 subjects will be enrolled in the SCCHN Cohort Expansion (Part 2). The null hypothesis that the true ORR is 25% will be tested against a 1-sided alternative: ORR = 40%. The null hypothesis will be rejected if 12 or more responses are observed in 35 subjects. This design gives a 1-sided type 1 error rate of 0.15 and a power of 0.81.

8.1.4 The SCCHN Randomized Cohorts (Part 3 - closed to enrollment)

The SCCHN Randomized Cohorts (Part 3) has a primary endpoint of ORR. A total of 225 subjects will be randomized in a 2:1 ratio to the 2 treatment arms, nivolumab combined with lirilumab (Arm A) and nivolumab monotherapy (Arm B), stratified by PD-L1 \geq 50% expression (yes/no) and prior treatment with cetuximab (yes/no).

Objective Response Rate:

The sample size is calculated to assess the ORR of lirilumab in combination with nivolumab. The type 1 error is set to 0.10 (2-sided) with no planned interim analysis. The final analysis for ORR will take place approximately 6 months after the last subject is randomized and treated. With 150 subjects in Arm A, if 50 responses are observed, the estimated ORR will be 33% and the 90% CI will be [26%, 41%]. In Study CA209041, the 90% CI for the nivolumab arm in PD-L1+ (> 1%) subjects was [9%, 25%].

The above sample size calculation was performed using EAST[®] 6 and SAS 9.2.

8.1.5 The Signal Detection Cohort Expansion (Part 4)

Removed with Revised Protocol 12.

8.1.7 The Signal Detection in Previously Untreated MEL with Lirilumab, Nivolumab, and Ipilimumab Combination (Part 6)

Removed with Revised Protocol 12.

8.2 Population for Analyses

- All Enrolled Data set: subjects who signed informed consent and registered in the study.
- All Treated Data set: all subjects who received at least 1 dose of any study drug.
- Response-Evaluable Data Set: all treated subjects who receive any study drug, have a baseline tumor assessment with measurable disease, and 1 of the following:
 - at least 1 evaluable on-treatment tumor assessment,
 - clinical progression, or
 - death prior to the first on-treatment tumor evaluation.
- Lirilumab PK Data Set: all subjects who receive at least 1 dose of lirilumab and have adequate serum concentration data for lirilumab PK.
- Nivolumab PK Data Set: all subjects who receive at least 1 dose of nivolumab and have adequate nivolumab PK.
- Lirilumab Immunogenicity Data Set: all subjects who receive at least 1 dose of lirilumab and have at least 1 ADA sample available.
- Nivolumab Immunogenicity Data Set: all subjects who receive at least 1 dose of nivolumab and have at least 1 ADA sample available.
- Ipilimumab Immunogenicity Data Set: all subjects who receive at least 1 dose of ipilimumab and have at least 1 ADA sample available.
- Biomarker Data Set: all treated subjects who have biomarker data available.
- For the SCCHN Randomized Cohorts (Part 3), Randomized Subjects Data Set: All enrolled subjects who were randomized. This is the dataset for baseline demographics and efficacy analyses for this cohort.
- For the SCCHN Randomized Cohorts (Part 3), PRO subjects: All randomized subjects with baseline and at least 1 post-baseline PRO assessment.

8.3 Endpoint Definitions

Endpoints are defined as follows.

Safety Endpoint Definitions

Safety is the primary endpoint in this study except for the SCCHN Randomized Cohorts (Part 3). All subjects who receive at least 1 dose of study drug will be evaluated for safety as measured by the occurrence of AEs, SAEs, deaths, and laboratory abnormalities, assessed during treatment and for 150 days in follow-up.

Study level endpoints used to assess the safety objective will be based on AE reports and the results of vital sign measurements, ECGs, physical examinations, imaging studies, and clinical laboratory tests. AEs will be categorized using the most current version of MedDRA; both AEs and laboratory tests will be graded using NCI CTCAE v4.03. All subjects who receive study drug therapy will be evaluated for safety as measured by the rate of AEs, and SAEs, and will be assessed during treatment and for 150 days in follow-up.

Safety will be measured by the following:

- Incidence of AEs: all non-serious AEs will be collected from Day 1 until 150 days after the subject's last dose of study drug or until they discontinue the study as per [Section 3.5](#) and all SAEs must be collected from the date of the subject's written consent until 150 days after discontinuation of dosing or until they discontinue the study as per [Section 3.5](#).
- Incidence of clinical laboratory test abnormalities including hematology and serum chemistry, and thyroid panel abnormalities, assessed at specified timepoints as designated in the Time and Events Section ([5.1](#)).

Efficacy Endpoint Definitions

Study level endpoints used to assess the anti-tumor activity objective are defined as follows:

ORR is defined as the total number of subjects whose BOR is either CR or PR divided by the total number of subjects in the population of interest.

PFS rate is defined as the probability of a subject remaining progression-free and surviving to 24 weeks. The probability will be computed based on the number of days between the first dose of study drug and PD or death, as defined by each criterion. For those subjects who remain alive and have not progressed, PFS will be censored on the date of the last tumor assessment. The above will be calculated based on tumor measurements occurring Q8W during treatment and at planned timepoints during the clinical follow-up period.

BOR is the best response designation recorded from the start of the study treatment until the end of treatment taking into account any requirement for confirmation, based on RECIST v1.1 criteria. CR or PR determinations included in the BOR assessment must be confirmed by a consecutive second (confirmatory) evaluation meeting the criteria for response that is performed at least 4 weeks after the criteria for response are first met. The above will be determined based on tumor measurements occurring Q8W (\pm 7days) during the treatment period (or Q6W (\pm 7days) for 1 year [48 weeks] and Q12W (\pm 7days) afterwards for the Signal Detection in SCCHN with Lirilumab, Nivolumab, and Ipilimumab Combination [Part 5] and once during the clinical follow-up period.

Other efficacy endpoints include the following:

OS is defined as the time from randomization to the date of death. A subject who has not died will be censored at last known date alive. OS will be followed continuously while subjects are on the study drug and every 3 months for up to 3 years following the first dose of study drug via in-person or phone contact after subjects discontinue the study drug.

PFS is defined as the time from randomization to the date of the first documented tumor progression (per RECIST v1.1). Subjects who die without a reported prior progression will be considered to have progressed on the date of their death. Subjects who did not progress or die will be censored on the date of their last evaluable tumor assessment. Subjects who did not have any on-study tumor assessments and did not die will be censored on the date they were randomized. Subjects who started any subsequent anti-cancer therapy without a prior reported progression will be censored at the last evaluable tumor assessment prior to initiation of the subsequent anti-cancer therapy.

DOR is defined as the time between the date of first confirmed response to the date of the first documented tumor progression (per RECIST 1.1), or death due to any cause, whichever occurs first. Subjects who neither progress nor die will be censored on the date of their last evaluable tumor assessment. Subjects who started any subsequent anti-cancer therapy without a prior reported progression will be censored at the last evaluable tumor assessment prior to or on initiation of the subsequent anti-cancer therapy. DOR will be evaluated for responders (confirmed CR or PR) only.

Time to response is defined as the time from randomization to the date of the first confirmed CR or PR. DOR will be evaluated for responders (confirmed CR or PR) only.

DCR is defined as the proportion of subjects with BOR equal to CR, unconfirmed CR, PR, unconfirmed PR, or SD.

Depth of response is defined as the target tumor burden percent change from baseline at nadir for each subject as measured by the percent of subjects with $\geq 50\%$ and $\geq 80\%$ tumor reduction

Pharmacokinetic Endpoint Definitions

PK endpoints (C_{max} [$\mu\text{g/mL}$], T_{max} [hr], AUC[0-T] [$\mu\text{g}\cdot\text{hr/mL}$], C_{trough} [$\mu\text{g/mL}$], AUC[TAU] [$\mu\text{g}\cdot\text{hr/mL}$], AUC[INF] [$\mu\text{g}\cdot\text{hr/mL}$], CL [L/day], T-HALF, V_z, and C_{min} [$\mu\text{g/mL}$]) will be evaluated using non-compartmental analysis, where feasible. In addition, nivolumab end of infusion and trough (C_{min}) concentrations will be calculated at specified visits for certain study parts [REDACTED].

Immunogenicity Endpoint Definitions

Endpoints for the study are incidence rates of persistent positive ADA as well as neutralizing positive ADA from initiation of each drug treatment and up to and including the follow-up period of the last study drug dosing. Based on recommendation from BMS Immunogenicity Council, Harmonization of Clinical Immunogenicity Reporting by an Initiative of the Therapeutic Protein Immunogenicity Focus Group of the American Association Pharmaceutical Scientists, and the

FDA Guidance for Industry Immunogenicity Assessment for Therapeutic Protein Products, the following definitions will be applied.

ADA Status of a Subject:

- Baseline ADA Positive Subject: A subject with baseline ADA positive sample
- ADA Positive Subject: A subject with at least 1 ADA positive sample relative to baseline at any time after initiation of treatment during the defined observation time period.
- ADA Negative Subject: A subject with no ADA positive sample after the initiation of treatment

Definitions for ADA Status of a Sample (Baseline ADA Positive, ADA Positive, or ADA Negative), as well as sub-categories of ADA Positive Subject such as Persistent Positive, Only the Last Sample Positive, Other Positive and Neutralizing Positive will be provided in the statistical analysis plan.

Biomarker Endpoint Definitions

Measures of TILs, PD-L1, [REDACTED] expression using IHC, including baseline and changes from baseline outcomes, on mandatory tumor biopsies from the subjects specified in each study part.

Quality of Life Endpoint Definitions

Quality of life endpoints are discussed in detail in [Section 5.8](#).

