3.5 Discontinuation of Subjects from Treatment

Subjects MUST discontinue investigational product (and non-investigational product at the discretion of the investigator) for any of the following reasons:

- Withdrawal of informed consent (subject's decision to withdraw for any reason)
- Any clinical AE, laboratory abnormality, clinical deterioration, or concurrent illness that in the opinion of the investigator indicates that continued participation in the study is not in the best interest of the subject
- Pregnancy
- Termination of the study by BMS
- Loss of ability to freely provide consent through imprisonment or involuntary incarceration for treatment of either a psychiatric or physical (eg, infectious disease) illness

- Documented and confirmed irPD as defined by irRECIST for the Dose Escalation and Cohort Expansion (Part 1; completed) and the SCCHN Cohort Expansion (Part 2; completed) (see [Appendix 2](#)).
- Documented PD for the SCCHN Randomized Cohorts (Part 3), and the Signal Detection in SCCHN with Lirilumab, Nivolumab, and Ipilimumab Combination (Part 5) as defined by RECIST v1.1 (see [Appendix 3](#)).
- Documented and confirmed irCR as defined by irRECIST for the Dose Escalation and Cohort Expansion (Part 1; completed) and the SCCHN Cohort Expansion (Part 2; completed) (see [Appendix 2](#)).
- Documented and confirmed CR for the Signal Detection in SCCHN with Lirilumab, Nivolumab, and Ipilimumab Combination (Part 5) as defined by RECIST v1.1 (see [Appendix 3](#)).
- Discretion of the investigator
- Inability to comply with the protocol requirements
- Protocol defined reasons for discontinuation (see [Section 4.9.5](#))
- Maximum treatment duration of up to a maximum of 2 years; 12 cycles in Parts 1, 2, and 3 or 8 cycles in Part 5.

In the case of pregnancy, the investigator must immediately notify the Sponsor or designee of this event. In most cases, the study drug will be permanently discontinued in an appropriate manner (eg, dose tapering if necessary for subject safety). Please contact the Sponsor or designee within 24 hours of awareness of the pregnancy. If the investigator determines a possible favorable benefit/risk ratio that warrants continuation of study drug, a discussion between the investigator and the Sponsor or designee must occur.

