All subjects who discontinue should comply with protocol specified follow-up procedures as outlined in [Section 5.1](#). The only exception to this requirement is when a subject withdraws consent for all study procedures or loses the ability to consent freely (ie, is imprisoned or involuntarily incarcerated for the treatment of either a psychiatric or physical illness).

If study drug is discontinued prior to the subject's completion of the study, the reason for the discontinuation must be documented in the subject's medical records and entered on the appropriate CRF page.

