5.3 Safety Assessments

AEs will be assessed continuously during the study and for 150 days after the last treatment or until the start of subsequent anti-cancer therapy. AEs will be coded using the most current version of the Medical Dictionary for Regulatory Activities (MedDRA) and reviewed for potential significance and importance. AEs will be evaluated according to the NCI CTCAE v4.03. Subjects should be followed until all treatment-related AEs have recovered to baseline or are deemed irreversible by the investigator.

Some of the assessments referred to in this section may not be captured as data in the CRF. They are intended to be used for safety monitoring by the treating physician. Additional testing or assessments may be performed as clinically necessary or where required by institutional or local regulations.

At baseline, a medical history will be obtained to capture relevant underlying conditions. Baseline signs and symptoms are those that are assessed within 2 weeks prior to subject registration. The baseline physical examination should include weight, height, heart rate, blood pressure, temperature and ECOG status and should be performed within 28 days of treatment assignment for the Dose Escalation and Cohort Expansion (Part 1) and the SCCHN Cohort Expansion (Part 2) and within 35 days of treatment assignment or randomization for all other study parts. Concomitant medications will be collected from within 2 weeks prior to treatment assignment or randomization through the study treatment period (see [Section 5.1](#)).

Subjects will be considered evaluable for safety if they have received any dose of either study drug. Toxicity assessments will be continuous during the treatment period and the clinical follow-up periods.

Body weight and performance status should be assessed at each on-study visit. Vital signs will be obtained at timepoints according to Section 5.1. For further details related to infusion reactions, see [Section 3.6](#).

Additional measures including non-study required laboratory tests should be performed as clinically indicated or to comply with local regulations. Laboratory toxicities (eg, suspected drug-induced liver enzyme evaluations) will be monitored during the clinical follow-up period via on-site/local laboratories until all study-drug-related toxicities resolve, return to baseline, or are deemed irreversible.

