6.1.1 Serious Adverse Event Collection and Reporting

Following the subject's written consent to participate in the study, all SAEs, whether related or not related to study drug, must be collected, including those thought to be associated with protocol-specified procedures. All SAEs must be collected that occur during the screening period and within 150 days of discontinuation of dosing. If applicable, SAEs must be collected that relate to any later protocol-specified procedure (eg, a follow-up skin biopsy).

The investigator should report any SAE occurring after these time periods that is believed to be related to study drug or protocol-specified procedure.

An SAE report should be completed for any event where doubt exists regarding its status of seriousness.

If the investigator believes that an SAE is not related to study drug, but is potentially related to the conditions of the study (such as withdrawal of previous therapy, or a complication of a study procedure), the relationship should be specified in the narrative section of the SAE Report Form.

SAEs, whether related or not related to study drug, and pregnancies must be reported to BMS (or designee) within 24 hours. SAEs must be recorded on the SAE Report Form; pregnancies on a

Pregnancy Surveillance Form (electronic or paper forms). When using paper forms, the reports are to be transmitted via email or confirmed facsimile (fax) transmission to:

SAE Email Address: See Contact Information list.

SAE Facsimile Number: See Contact Information list.

For studies capturing SAEs/pregnancies through electronic data capture (EDC), electronic submission is the required method for reporting. The paper forms should be used and submitted immediately, only in the event the electronic system is unavailable for transmission. When paper forms are used, the original paper forms are to remain on site.

SAE Telephone Contact (required for SAE and pregnancy reporting): See Contact Information list.

If only limited information is initially available, follow-up reports are required. (Note: Follow-up SAE reports should include the same investigator term(s) initially reported.)

If an ongoing SAE changes in its intensity or relationship to study drug or if new information becomes available, a follow-up SAE report should be sent within 24 hours to BMS (or designee) using the same procedure used for transmitting the initial SAE report.

All SAEs should be followed to resolution or stabilization.

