4 ENDPOINTS

4.1 Primary Endpoints

Safety and preliminary anti-tumor activity are the primary objective for all parts (i.e. Parts 1, 2, 3, and 5) except Part 1, where the primary objective is to assess the safety and tolerability of lirilumab given in combination with nivolumab, and Part 3, where the primary objective is to assess estimate the objective response rate of lirilumab given in combination with nivolumab.

For safety objective, all subjects who receive at least 1 dose of study drug will be evaluated for safety as measured by the incidence of AEs, SAEs, AEs leading to discontinuation, and deaths assessed during treatment and for 150 days in follow-up. In addition, clinical laboratory test abnormalities will be examined.

All non-serious AEs will be collected from Day 1 until 150 days after the subject's last dose of study drug or until they discontinue the study as per study protocol Section 3.5 and all SAEs must be collected from the date of the subject's written consent until 150 days after discontinuation of dosing or until they discontinue the study as per study protocol Section 3.5. AEs will be categorized

using the most current version of MedDRA. AEs and laboratory values will be graded according to the National Cancer Institute (NCI) Common Terminology Criteria for Adverse Events (CTCAE) version 4.03.

For preliminary-antitumor activity, the primary endpoint will be to estimate ORR by derived BORs per RECIST v1.1 using investigator-provided tumor assessments for all Parts. The BORs for investigator-assessed responses per RECIST v1.1 for Parts 3 and 5 will be listed. Details regarding the definition of ORR will be given in the upcoming Secondary endpoint section for preliminary antitumor activity.

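### Protocol and SAP give conflicting end dates for AE and SAE collection, and the SAP's AE rates count follow-up time in which non-serious events need not be collected

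*Protocol*

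**What the plan says.** Safety is the primary endpoint in every part except Part 3 (Protocol 8.3). The end of event collection is stated in several places.

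- **Protocol 5.3**, repeated in the synopsis, gives this rule: "AEs will be assessed continuously during the study and for 150 days after the last treatment or until the start of subsequent anti-cancer therapy". There is no limit to non-serious events.
- **Protocol 6.1.1**: "All SAEs must be collected that occur during the screening period and within 150 days of discontinuation of dosing". It adds that any later SAE believed related to study drug or to a protocol procedure should also be reported.
- **Protocol 5.1**, on-treatment and follow-up tables for Parts 1/2, 3 and 5: non-serious AEs stop at 150 days or new anti-cancer therapy; SAEs run to 150 days with no such stop.
- **Protocol 8.3**: non-serious AEs are collected until 150 days after the "last dose of study drug or until they discontinue the study as per" Section 3.5, and SAEs "until 150 days after discontinuation of dosing or until they discontinue the study as per" Section 3.5. New therapy is not mentioned.
- **SAP 4.1** repeats that rule; for SAEs it reads "150 days after discontinuation of dosing or until they discontinue the study as per study protocol Section 3.5".
- **Protocol 3.5**, the section pointed to, is titled "Discontinuation of Subjects from Treatment".

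On the analysis side, SAP 7.6 summarizes AEs to 150 days after the last dose for subjects off treatment, with no cut at new therapy. SAP 7.6.7 computes rates per 100 patient-years. It adds 100 post-dose days to exposure for subjects followed at least that long, or 150 for those followed for 150. SAP 7.6.8 takes laboratory results to 100 or 150 days, although SAP 7.6 gives 150.

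**The concern.** A site and a programmer need one answer to two questions: until when is a non-serious AE recorded, and until when is an SAE recorded? The documents give more than one answer to each.

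For SAEs, a site working from 5.3 could stop at new therapy, while 6.1.1 obliges it to continue. Events left unrecorded may not be recoverable later.

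For non-serious AEs, the tables and 5.3 allow collection to stop at new therapy. The endpoint definition in 8.3 and SAP 4.1 does not, and the SAP analysis windows ignore the stop. Time after new therapy then enters the denominator of an exposure-adjusted rate although its non-serious events need not have been recorded. That pulls the rate down.

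**Working it through.** The plan states no figure to reproduce; this is a check of text against text. Last treatment, last dose and discontinuation of dosing are treated as the same day. Where a rule joins two end points with a bare or, I take the earlier. That is an assumption, since none of the rules says so.

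| Place | Non-serious AEs end at | SAEs end at |
|---|---|---|
| Protocol 5.3, synopsis | 150 days or new therapy | 150 days or new therapy, as worded |
| Protocol 5.1 tables | 150 days or new therapy | 150 days |
| Protocol 6.1.1 | not covered | 150 days, later if believed related |
| Protocol 6.2.1 | start given, no end | not covered |
| Protocol 8.3, SAP 4.1 | 150 days or leaving the study per 3.5 | same |
| SAP 7.6 (summaries) | 150 days, no cut | 150 days, no cut |

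Protocol 8.3 and SAP 4.1 count as one rule.

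**Days in dispute.** Let n be the day after last dose on which new therapy starts. The documents give no value, so n is assumed.

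- SAEs: 5.3 gives min(150, n); 6.1.1 and the tables give 150. The gap is 150 − min(150, n): 136 days at n = 14, 120 at n = 30, 90 at n = 60, and 0 from n = 150 on.
- Non-serious AEs: 5.3 and the tables give min(150, n). Protocol 8.3 and SAP 4.1 give 150 for a subject who has not left the study. The gap is the same.

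**Effect on the SAP 7.6.7 rate.** Let T be last dose date minus first dose date. For a subject off treatment and followed, exposure is T + 150 + 1 days (or T + 100 + 1). If non-serious events are recorded only to day n, the observed time is T + n + 1. With a constant event rate (an assumption), the reported rate is the true rate times (T + n + 1)/(T + 151), or (T + n + 1)/(T + 101).

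T follows from the 8-week cycle with the last nivolumab dose on Day 43. One cycle gives 43 − 1 = 42 days. Twelve cycles give 11 × 56 + 42 = 658 days.

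| T | n | with 150 days | with 100 days |
|---|---|---|---|
| 42 | 14 | 57/193 = 0.30 | 57/143 = 0.40 |
| 42 | 60 | 103/193 = 0.53 | 103/143 = 0.72 |
| 658 | 14 | 673/809 = 0.83 | 673/759 = 0.89 |
| 658 | 60 | 719/809 = 0.89 | 719/759 = 0.95 |

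These are factors for one affected subject and for non-serious events only. They are not estimates for the study. SAP 7.6.7 calls its numerator on-treatment events without restating a window; I have used the SAP 7.6 window.

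**The case against.** **The more detailed text handles SAEs consistently.** The follow-up tables and 6.1.1, where a site would look, agree on 150 days. Section 6.1.1 also catches later SAEs judged related, so what 5.3 could lose is mainly SAEs judged unrelated. The Revised Protocol 12 change summary describes the new cut-off as concerning non-serious AEs, which suggests a missing word in 5.3 (though its rationale column speaks of AE collection generally). This stands as evidence of intent, but it does not alter what 5.3 and the synopsis now say.

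**A stronger reading fails.** Because 8.3 and SAP 4.1 point to the treatment-discontinuation section, and every subject eventually meets one of its reasons, a reader might infer that collection ends with treatment and that nobody gets the 150 days. The documents do not support that:

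- The clause speaks of leaving the study, not of stopping drug.
- Section 3.5 closes with "All subjects who discontinue should comply with protocol specified follow-up procedures as outlined in" Section 5.1. Its only exceptions are withdrawal of consent for all procedures and loss of the ability to consent freely. Section 3.7.1 draws the same line.
- Section 8.3 itself, the visits on Days 30, 60, 100 and 150, and SAP 6.1 all keep the 150-day follow-up.
- The stated total of about 2.5 years fits a full follow-up: 12 × 8 × 7 = 672 treatment days, plus 150, plus 28 to 35 of screening, is 850 to 857 days, or 2.33 to 2.35 years.

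**The rate bias may be small.** SAP 7.6.7 tables cover Parts 1 and 2 only, and the change summary dates the new-therapy wording to Revised Protocol 12. Only subjects whose follow-up ran past its implementation are exposed to it. The documents do not say how many. Likewise, 100 or 150 days is probably a remnant of the 150-day follow-up having been added by Amendment 12.

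**Conclusion.** The contradiction is real. Section 5.3 and the synopsis conflict with 6.1.1 and the Section 5.1 tables on SAEs. Protocol 8.3 and SAP 4.1 conflict with 5.3 and the tables on non-serious AEs. The pointer to Section 3.5 is a loose cross-reference that should be corrected, not a rule that removes follow-up.

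The size depends on when subsequent therapy starts. Up to 136 of 150 days are in dispute at an assumed start on day 14, and none if it starts after day 150. For an affected subject under a constant rate, the non-serious AE rate in SAP 7.6.7 would be reported at roughly 0.30 to 0.95 of its true value over the assumed range. The study-level effect cannot be computed from the documents and may be modest. Its direction, where it occurs, is downward.

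**What to change.** Reconcile the passages.

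1. **Protocol 5.3 and synopsis:** limit the new-therapy cut-off to non-serious AEs, to match 6.1.1 and the tables, and say whichever is earlier.
2. **Protocol 8.3 and SAP 4.1:** add the same cut-off for non-serious AEs. Replace the general pointer to Section 3.5 with withdrawal from follow-up, as in the closing text of 3.5 and in 3.7.1.
3. **SAP 7.6 and 7.6.7:** count non-serious AEs, and the exposure time that goes with them, to the earlier of 150 days or subsequent therapy. Count SAEs and deaths to 150 days.
4. **SAP 7.6.7 and 7.6.8:** replace the open choice of 100 or 150 days with one stated rule that agrees with SAP 7.6. If earlier subjects had only 100 days of follow-up, say which.

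The cost is wording in two protocol sections, the synopsis and four SAP sections, plus a second exposure calculation. The downside is that the SAP must describe two windows, and any table that mixes serious and non-serious events must state which applies.
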